11.2 Adequacy of Protection Against Risk

11.2.1 Physical risks

The BP cuffs could cause skin irritation or bruising – this is unlikely given the FDA approved devices used and will most likely be of low seriousness. In addition, it is possible that the participants will experience a medical emergency and elect to text the research number instead of seeking care. All text messages sent into the Reach Out system will receive a standard message similar to, “Remember: this is an automated messaging system, and texts other than your BP are not read. If you have questions, ask your [name] this is an emergency call 911.”

If BP received is outside of parameters, participants will receive something akin to the following message, “You sent a BP that is very high or low. If this is right, please contact a Dr. very soon to check your BP. If you sent it by accident, please text us a new BP.”

11.2.2 Psychological risks

We do not anticipate our intervention will induce psychological risks. We provide positive text messages and referrals to primary care providers. There is a small risk that our study team will lose or release private personal health information and that this could induce psychological harm. We are not collecting sensitive health information that could lead to psychological harm if disclosed to unauthorized individuals.

11.2.3 Financial risks

Text-messaging charges could create a financial burden on participants. We plan to minimize this risk by specifically discussing this during the enrollment process. In addition, our previous work demonstrates that the majority of eligible patients will have unlimited text messaging plans. We do not use any sort of app or data (which is more likely to incur costs for participants). Additionally, we believe it will be unlikely that anyone will have limited minute mobile voice plans, and thus it will be unlikely that our study protocol will induce overage fees for participants. Additional financial risks would include identity theft due to the loss of sensitive information by the study team; we are minimizing the personal data that we collect to what is necessary for our research strategy so this should be unlikely.

11.2.4 Legal risks

We are not collecting location-based data relating to text messages and we do not anticipate that our research protocol will induce any additional legal risks for participants. Alternative procedures that may confer less risk: we are conducting a prospective, clinical trial of several low risk interventions to improve BP. Alternatives to our research strategy would generally be for the participants to self-monitor their BP and follow up with their doctors outside of our protocol. This will be included as an alternative to participation during the informed consent process.

11.3 Institutional Review Board (IRB) Review and Informed Consent

This protocol and the consent and any subsequent modifications will be reviewed and approved by the IRB or ethics committee responsible for oversight of the study.

11.4 Participant Confidentiality / Data Retention

All records will be kept in a locked file cabinet or on secure computer systems. Clinical information will not be released without written permission of the participant, except as necessary for monitoring by IRB, the FDA, or the NIMDH. In accordance with NIH regulations, we may create a permanent de-identified, public use database. We will remove linkages to protected health information, hospital identifiers and patient identifiers. The purpose of the retention of this data is for future research and to comply the NIH regulations for datasets created during the conduct of NIH funded research grants.

11.5 Study Modification/Discontinuation

The study may be modified or discontinued at any time by the IRB, the NIMDH, or other government agencies as part of their duties to ensure that research participants are protected.

Appendix A – Flyer for taking your BP at Home

Instructions for Taking Your Blood Pressure (BP) at Home

It is helpful to check your blood pressure throughout the week because your BP can go up and down. You should try to take your BP a total of 4 times each day:

[figure not shown]
- Take your BP 2 times in the morning, before you eat breakfast & before taking your medications for the day.
- Take your BP again 2 times in the evening, an hour before eating dinner.

- 1 Don't drink anything (coffee, pop, or alcohol), smoke, or workout within 1 hour of taking your BP.
- 2 Sit down and rest for at least 5 minutes before taking your BP.
Sit calmly and don't talk.
- 3 Place your left elbow on a table so that the monitor will be at the same level as your heart. Keep your feet flat on the floor and don't cross your legs
- 4 Wrap the cuff securely around your left wrist. Push the power button to turn the machine on. The cuff will automatically inflate and measurement will start.
- 5 Wait 1 minute as the cuff automatically deflates, then push the power button again. You should have taken your BP a total of 2 times.
- 6 Reply to your REACH OUT text message with your first BP. You can see on the screen the BP was 120/80.

REACH OUT
For Lower Blood Pressure

Important: The text messages are not read by medical providers, so never text medical questions. If you are having an emergency, please call 911

Have questions about REACH OUT study? Call or text the REACH OUT staff at [contact]

Appendix B – Blood Pressure Informational flyers

ANSWERS by heart | Lifestyle + Risk Reduction High Blood Pressure

What Is High Blood Pressure Medicine?

Your doctor has prescribed medicine to help lower your blood pressure. You also need to make the other lifestyle changes that will help reduce blood pressure, including: not smoking, reaching and maintaining a healthy weight, lowering sodium (salt) intake, eating a heart-healthy diet including potassium-rich foods, being more regularly physically active, and limiting alcohol to no more than one drink a day (for women) or two drinks a day (for men). Following your overall therapy plan will help you get on the road to a healthier life!

What should I know about taking medicine?

- Your doctor may prescribe one or more drugs to bring your blood pressure down to normal.
- The medicines work in different ways to help lower blood pressure.
- Medicine only works when you take it regularly.
- Don't ever stop taking medicine on your own.
- Even after your blood pressure is lowered, you may still need to take medicine — perhaps for your lifetime — to keep your blood pressure normal.

How can I remember to take it?

Sometimes it's hard to keep track of your medicine. But to be safe, you must take it properly. Here are some good ways:

- Take your medicine at the same time each day.
- Take medicine along with daily events, like brushing your teeth.

(continued)

BLOOD PRESSURE

KNOW YOUR NUMBERS

BLOOD PRESSURE is the force of your blood moving against the walls of your arteries. It's expressed as **TWO NUMBERS**:

Top Number: SYSTOLIC (mm Hg)
The pressure or force in the arteries when the heart beats

Bottom Number: DIASTOLIC (mm Hg)
The pressure measured between heartbeats

WARNING! Over time elevated or high blood pressure weakens your heart, blood vessels and kidneys, and makes a stroke or heart attack much more likely

LIFESTYLE CHANGES that Lower Blood Pressure

- Move More** Get regular physical activity
- Focus on Nutrition** Follow the DASH diet and eat potassium-rich vegetables
- Cut Salt** Aim for 1,500 mg of sodium or less per day
- Limit Alcohol** For men, no more than 2 drinks per day; for women, 1
- Loss Weight** Losing just a few pounds can make a big difference
- Don't Smoke** If you smoke, stop
- De-stress** Meditation and rest help lower blood pressure

BLOOD PRESSURE CHART

Category	Normal	Elevated	High
NORMAL	below 120 below 80	120 to 129 below 80	130 to 139 80 to 89
ELEVATED			STAGE 1: 140 and above STAGE 2: 90 and above
HIGH			Also called Hypertension

Information provided for educational purposes only. Please consult your health care provider about your specific health needs.

Go to CardioSmart.org/HighBP to learn more about High Blood Pressure.

© 2014 American College of Cardiology Foundation. All rights reserved. CardioSmart.org

Appendix D – Sample text messages

	Theory	Construct	Category	Subcategory	Text Message
1.	Social Cognitive Theory (SCT)	COGNITIONS (Knowledge/Skills)	DIET	Substitutions	If you're trying to limit your sugar, try switching soda, lemonade, and other juices for water! Carrying a water bottle throughout the day can help you drink more!
2.	SCT	COGNITIONS Knowledge/Skills	DIET	Substitutions	Canned products can have a lot of salt! Look for "lower sodium" or "salt-free" varieties at the grocery store instead!
3.	SCT	COGNITIONS Knowledge/Skills	DIET	Culinary Knowledge	Rinsing canned veggies and beans with water after you open them can help remove extra salt!
4.	SCT	COGNITIONS Self-Efficacy	DIET	Eating/ Ordering out	Salads are a healthy option especially when eating out. Beware of the extra toppings though and try asking for the dressing and cheese on the side so you can choose how much to add!
5.	SCT	COGNITIONS Self-Efficacy	DIET	Planning	Planning your meals can be a great way to help you stay on track! Start with planning one of your meals for the week like lunch or dinner!
6.	SCT	COGNITIONS Self Efficacy	DIET	Eating/ Ordering Out	Try asking your server when out restaurants if you can substitute steamed vegetables or fruit for French fries and chips
7.	SCT	COGNITIONS Self Efficacy	DIET	Snacks	We all have cravings once in a while. Try a piece of fruit or yogurt with granola as a healthy substitute for ice cream or cookies!
8.	SCT	COGNITIONS Self Efficacy	DIET	Eating/ Ordering Out	Find yourself struggling to find healthy options at fast food restaurants? Try to choose baked or grilled options over items that are fried to keep calories from fat down!
9.	SCT	COGNITIONS Outcome Expectations	DIET	Eating/ Ordering Out	Portion sizes at restaurants can be really large. Try asking your server to box up half of your meal before it gets to the table!
10.		COGNITIONS Outcome Expectations	DIET	Food Access	If you find fruits and veggies going bad before you use them, opt for buying frozen ones! Frozen has the same amount of nutrients as fresh!

11.	SCT	SOCIOENVIRONMENTAL Social Support	DIET	Encouragement	Stress can make it hard to eat healthy and exercise, try talking with friends and family about your health goals to help keep you on track! ☺
12.	SCT	SOCIOENVIRONMENTAL Social Support	DIET	Food Access	Check out your local farmers market for fresh fruits and veggies! Follow this link to find the closest market to your home –
13.	SCT	SOCIOENVIRONMENTAL Social Support	DIET	Food Access	Did you know some farmers markets accept SNAP EBT vouchers? Check with your local market and vendors to see if you can use your benefits to buy fresh produce!
14.	SCT	BEHAVIORAL Reinforcement	DIET	Encouragement	Eating healthy is hard! You are doing a great job, keep at it! ☺
15.	SCT	BEHAVIORAL Reinforcement	DIET	Culinary Knowledge	Cooking at home not only helps you save money, but is generally healthier than eating out because you decide how much sugar, salt and fat to add!
16.	SCT	Reinforcement	DIET	Encouragement	All of us here on the REACH OUT team are proud of the progress you have made. Keep up the great work! ☺
17.	SCT	Reinforcement	DIET	Encouragement	Stress can make eating healthy seem overwhelming and hard. Keep at your health goals and try to take it one day at a time! ☺
18.	SCT	BEHAVIORAL Reinforcement	DIET	Eating/ Ordering Out	Eating healthy at restaurants can be challenging. Most restaurants have their menus available online so try checking these out beforehand so you can plan for success even when eating out! ☺
19.	SCT	Reinforcement	PHYSICAL ACTIVITY	Exercising regularly is hard! You are doing a great job, keep at it! ☺	
20.	SCT	Social Support	PHYSICAL ACTIVITY	Accountability helps with sticking to eating healthy and being active! Find a friend, family member, or significant other that you can share your goals with to help keep you on track!	
21.	SCT	Social Support	PHYSICAL ACTIVITY	Work days are long and exhausting! Try turning your lunch hour into a daily walk! Bring along a co-worker and turn it into a social hour!	

22.	SCT	Knowledge	PHYSICAL ACTIVITY	An easy way to get more steps into your day is by opting to take the stairs over the elevator when you can!
23.	SCT	Outcome Expectations	PHYSICAL ACTIVITY	Weight loss can be challenging! But maintaining a healthy weight can make it easier to do things like cook, work, and even play with your kids/grandkid! ☺
24.	SCT	Knowledge	PHYSICAL ACTIVITY	Winter can make getting outside challenging. If you find yourself struggling to be active outdoors, consider trying a new winter activity with friends like skiing, ice skating, or snow shoeing!
25.	SCT	Outcome Expectations	PHYSICAL ACTIVITY	If your job involves a lot of sitting, try to schedule 15 minutes every couple of hours to walk around! Take the longer route to the bathroom, the stairs, or even a lap around the building!
26.	SCT	Reinforcement	PHYSICAL ACTIVITY	Stress can make exercise seem overwhelming and hard. Keep at your health goals and try to take it one day at a time! ☺
27.	SCT	Knowledge	PHYSICAL ACTIVITY	Try using commercial breaks while watching TV as a time to get up and get moving! Try doing some, lunges, jumping jacks or jogging in place!
28.	SCT	Knowledge	PHYSICAL ACTIVITY	Don't forget that being active can be more than going for a run or hitting the gym! Try gardening, biking, or even a walk to get yourself up and moving!
1.	SCT	MEDICATION ADHER- ANCE		It is very important to regularly take your BP medication, get help by asking people close to you to remind you. Often the more support you have the better!
2.	SCT	MEDICATION ADHER- ANCE		Don't forget to regularly take your BP meds, and do not stop any medications without talking to your health care provider first. Consistency is very important!
3.	SCT	MEDICATION ADHER- ANCE		Remember to take your BP meds every day. If you don't feel like your meds are making a difference, or you're having side-effects, your Dr can help, go see them!
4.	SCT	MEDICATION ADHER- ANCE		Often cost of BP meds are a challenge, but there are discount, BPmeds at many stores, such as Kmart, Meijer, Walmart, CVS, and Walgreens.
5.	SCT	MEDICATION ADHER- ANCE		Many stores like Kmart, Meijer, Walmart, CVS, and Walgreens provide discounted BP meds. Save money by checking to see if your BP meds are cheaper there.

6.	SCT	MEDICATION ADHER- ANCE	If you find yourself having trouble remembering to take your BP meds, use a beeping alarm or watch to remind you when a dose is due, and to keep consistency!
1.	SCT	Med Encouragement	It's not always easy to decide when it's time to start taking BP meds, but most people need meds in addition to exercise and diet to lower their high BP.
2.	SCT	Med Encouragement	Often cost of BP meds are a challenge, but there are discount, generic meds at many stores, such as Kmart, Meijer, Walmart, CVS, and Walgreens.
3.	SCT	Med Encouragement	Think about how important it is to you to lower your BP, then start taking small steps towards change. One important step may be beginning BP medication.
4.	SCT	Med Encouragement	If your healthy habits aren't enough to bring your BP below 140/90, you may need to take BP medication, and this is something a Dr can help you decide.
5.	SCT	Med Encouragement	It is important to consider talking about BP meds with a [name] people who take pills for high BP need to take 2 or more kinds of pills that work together.
6.	SCT	Med Encouragement	If you are like most people with high BP, meds can play a major part in lowering your BP. It is between you and a Dr to determine the right plan.
7.	SCT	Med Encouragement	Though healthy life changes are key to lower your BP, it may also be key to take BP meds with a [name] you don't have one, you can call Hamilton [contact].
8.	SCT	Med Encouragement	Many stores like Kmart, Meijer, Walmart, CVS, and Walgreens provide discounted BP meds. Save money by checking to see if your BP meds are cheaper there.
9.	n/a	Coronavirus Impact	Have you been diagnosed with COVID-19 (i.e., coronavirus infection)? Have any of your family or friends been diagnosed with COVID-19 (i.e., coronavirus infection)? Have you had fevers, cough, runny nose, shortness of breath, cold-like symptoms, or flu-like symptoms in the last week? Have you received your flu shot this year?

Special Messages		
Welcome to REACH OUT- first text sent out to everyone	156	Welcome to REACH OUT! You will text in your BP once a week and get feedback/tips on how to better manage your high BP. Save this number into your contacts!
Weekly BP Survey Collection	157	This is your weekly reminder to take your BP and reply back to this message. If you have questions see your BP cuff instructions, and the REACH OUT handout.
Not real BP number- an unrealistic number was sent in.	153	The BP you sent in does not seem to be right. Your BP should setup like xxx/xxx. Refer to your BP cuff instructions, and the home BP measurement handout.
Reminder: Did not text in BP reading (After waiting 3 hours)	124	Remember to text in your weekly BP reading so we can create personalized messages for you this week based on your progress.
	152	Don't forget to text in your BP this week. If you have any questions about taking your BP see your BP cuff guide, and the REACH OUT handout we gave you.
	159	Remember to text in your BP reading so we can create personalized messages for you this week based on your progress. This is your last reminder for this week.
Text something other than BP	160	Remember: this is an automated messaging system, and texts other than your BP are not read. If you have questions ask your [name] this is an emergency call 911
Success Response: what to send back	159	REACH OUT has received your BP of \$current-blood-pressure . Thank you for your response, now you can get personal messages on your most current BP for the week!

when they do enter a valid BP		
BP greater than 180/110	148	
You recently reported a BP greater than 180/110, which is very high. Please contact a Dr. soon (at least within a few days) to have your BP checked.
 
Note: Bottom number (diastolic) larger than top number (systolic)
 
Parameters:
 
top number (systolic) less than 70 or greater than 250 Bottom number (diastolic) less than 50 or greater than 140

If they were outside the BP parameters	158	You sent a BP that is very high or low. If this is right, please contact a Dr very soon to check your BP. If you sent it by accident, please text us a new BP.
If diastolic bigger than systolic	159	The BP you sent in does not seem to be right. Your BP should be like xxx/xxx. Refer to your BP cuff instructions, and the home BP handout. Please text new BP.
If they text back the same number	155	You recently sent a BP that is extremely high or low. If this was the actual reading given by the machine, please contact a Dr very soon to check your BP.
Closing		You have been in the research study, REACH OUT, for about 4 months. Please send in your final blood pressure through text message!

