The text-messaging system may make up to a total of 3 attempts until the participant responds with a BP. Some messages for that week may then be tailored on that BP recording.

Please note this will be the only Reach Out research specified outbound message that will be permissible from the participants to the research team. Otherwise, messages sent by the participant will trigger an automated response saying that the response is automated and that for emergencies, the participant should call 911. Participants who have a BP >180/120 will be sent an automated message telling them to call their doctor right away, as they likely need more or different medication, and if they have symptoms such as chest pain, weakness, difficulty talking, or confusion to call 911.. Additionally, if a message is sent to the system that doesn't make sense in the context of a BP reading, an automated error message will be sent back for them to resubmit their BP in the previously taught method.

Participants will have the option to modulate their own reminder frequency by texting prompts to either receive daily BP message reminders, weekly message reminders, or setting them back to where they were assigned at baseline.

6.1.3 **Facilitated primary care provider appointment scheduling and transportation**

Recognizing the importance of primary care provider visits and transportation, Reach Out will facilitate primary care provider appointment scheduling and transportation. Participants will be randomized to receive either facilitated scheduling and transportation, or passive reminders.

Participants randomized to the facilitated group will be able to schedule appointments with their primary care provider via phone call or text capability, which may be facilitated by the research team depending on the capability of our scheduling system. If a provider office indicates that they require proof of permission from participant regarding the ability to schedule appointments

on their behalf, REACH OUT may provide that to them for their files, or complete the office's specific permission forms (Appendix H).

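### The high-BP replies printed in Appendix D and section 11.2.1 are weaker than the reply section 6.1.2 promises above 180/120

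*Protocol*

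**What the plan says.** Section 6.1.2 (prompted BP self-monitoring) states the rule in the main text: "Participants who have a BP >180/120 will be sent an automated message telling them to call their doctor right away". The same sentence adds that "if they have symptoms such as chest pain, weakness, difficulty talking, or confusion to call 911".

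Appendix D, under Special Messages, prints three replies that a high reading could trigger:

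- The high-BP row: "You recently reported a BP greater than 180/110, which is very high", followed by "Please contact a Dr. soon (at least within a few days) to have your BP checked".
- The out-of-parameter row, for systolic below 70 or above 250, or diastolic below 50 or above 140: "You sent a BP that is very high or low. If this is right, please contact a Dr very soon to check your BP". It then asks for a new reading if the first was sent by accident.
- The row for the same number texted back: "If this was the actual reading given by the machine, please contact a Dr very soon to check your BP".

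Section 11.2.1 (physical risks) repeats the out-of-parameter reply, introduced by "If BP received is outside of parameters, participants will receive something akin to the following message". The heading of Appendix D calls its contents "Sample text messages".

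**The concern.** The automated reply is the protocol's safety response to a dangerous texted reading. The flyers in Appendices A and E tell participants that medical providers do not read the texts. Severe readings are foreseeable: entry requires systolic of at least 160 or diastolic of at least 100 in the ED, then an elevated self-reported reading in the eligibility phase, and participants text readings daily or weekly for 12 months.

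If the Appendix D texts are the ones sent, a participant who texts 185/125 is told to make contact within a few days and hears nothing about symptoms or 911. Section 6.1.2 promises that participant more urgent advice. For an extreme reading such as 255/145, the printed reply says very soon, and the reader cannot tell whether the section 6.1.2 message is sent too.

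**Working it through.** The plan gives no figure to reproduce, so the check sets the texts side by side.

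| Place | Trigger | Urgency of contact | 911 for symptoms |
|---|---|---|---|
| Section 6.1.2 | above 180/120 | at once | yes |
| Appendix D, high-BP row | above 180/110 | within a few days | no |
| Appendix D, out-of-parameter row | systolic <70 or >250, diastolic <50 or >140 | very soon | no |
| Appendix D, same-number row | same value sent again | very soon | no |
| Section 11.2.1 | outside parameters | very soon | no |

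**Content.** Of the three Appendix D replies, 0 of 3 say to call the doctor at once, and 0 of 3 mention 911 or any symptom named in section 6.1.2. The only Appendix D text with 911 answers a message that is not a BP. Wording close to section 6.1.2 does appear in Appendix F, but that is a feedback sheet for a BP taken by the study, not a reply to a texted reading.

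**Triggers.** Neither place says whether one or both numbers must exceed the limit. Under either convention, a reading above 180/120 is also above 180/110, so it meets the printed high-BP trigger and the printed advice is the weaker one. Take 185/125: 185 > 180, 125 > 120 and 125 > 110, so it meets both triggers whichever convention is used.

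For readings inside the parameters, the two triggers disagree on whether to alert only at diastolic 111 to 120:

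- if either number suffices, when systolic is 180 or lower (for example 150/115);
- if both are needed, when systolic is 181 to 250.

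**Extreme readings.** For 255/145, 255 > 250 and 145 > 140, so it is out of parameter. Also 255 > 180 and 145 > 120, so it meets the section 6.1.2 trigger. The documents do not say whether one reply or both would go out.

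**Coverage of the fix.** Simply replacing the 180/110 row with a 180/120 row would, if either number suffices, remove the only printed alert for readings such as 150/115. Keeping the present text for readings above 180/110 that do not meet the 180/120 trigger avoids this. With one convention for both limits, the two groups together make up everything above 180/110, so no reading now alerted is lost.

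**The case against.** The strongest reply is that absence from Appendix D proves little. The list is headed as samples, and section 6.1.1 allows messages to be added. It is visibly incomplete: its BP prompts are weekly only, although half the arms are prompted daily, and it has no appointment texts or outcome-visit reminders. Its closing row speaks of about 4 months in a 12-month trial, which looks like leftover text. On this view section 6.1.2 is the operative rule, Appendix F agrees with it at 180/120, and the 180/110 row is simply out of date. All of this stands. It limits the point to a mismatch in the written messages, but the mismatch remains.

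A reader might infer that participants with severe readings were in fact sent the weaker advice. The documents do not support that, because they do not show which text was programmed.

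A reader might also infer that the out-of-parameter reply contradicts section 6.1.2 outright at 255/145. That is too strong. The out-of-parameter row asks for a resend and works mainly as an entry check, and the same-number row appears to be its follow-up. Section 6.1.2 itself has a separate error reply for messages that make no sense as a BP. Nothing says these replies exclude the urgent message. What stands is an ambiguity, and it reaches section 11.2.1 in the main text, whose introductory words allow rewording but do not say that symptom or 911 advice is added.

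The emergency 911 line on the Appendix A and E flyers gives partial cover. It names no symptoms and is not sent in reply to a reading.

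**Conclusion.** The inconsistency is real and should be corrected. The one printed high-BP alert differs from section 6.1.2 in trigger (180/110 against 180/120), in urgency (a few days against at once) and in lacking symptom and 911 advice. For extreme or repeated high readings the written plan is unclear, not demonstrably contradictory.

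Confidence is high for the textual mismatch. Any consequence for participants depends on the Appendix D wording having been programmed, which is unknown. How often such readings occur cannot be derived from the documents. The sample size, estimand and primary analysis are unaffected.

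The chance to change live messages may have passed. Section 3 gives March 2019 to August 2020 as the comparison period for the intervention, and this protocol version is dated 1 August 2022. Even if August 2020 were only the end of enrolment, 12 months on is August 2021, and 18 months for the cognition supplement is February 2022. That timing is an inference from those dates.

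**What to change.** 1. Add the section 6.1.2 message to Appendix D for BP above 180/120, with both the instruction to call the doctor at once and the 911 advice for symptoms.
2. Keep the few-days text only for readings above 180/110 that do not meet the 180/120 trigger.
3. State in Appendix D and section 11.2.1 that an out-of-parameter or repeated high reading also gets the section 6.1.2 advice, alongside the request to resend. Low readings can keep the present texts.
4. State whether one or both numbers must exceed the limit, in section 6.1.2 and Appendix D alike. The documents do not settle this, and the choice is the sponsor's.
5. Check the platform set-up or the sent-message log for the text actually used, and record the answer.

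The cost is a few edited rows in Appendix D and a clause each in sections 6.1.2 and 11.2.1. Section 2.1.2 gives 160 characters as the length of a text, so the wording must be drafted to fit. The downside is that a mistyped extreme reading may prompt urgent advice, which is why the resend request should stay. The cost of the platform check is not known. If message delivery has ended, only step 5 and correction of the record remain.
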